10.1. Randomization Procedure

Using computer generated randomization, the randomization process will be stratified by race and sex and blocked to ensure balance at random accrual points. Lists were compiled for the 4 sex-race specific strata. As new participants are added to the study they will be assigned the next available treatment assignment (CBCR, HYCR) based on the lists provided. The project manager will be responsible for treatment assignment as all other staff involved in the study will be blinded as to the randomization lists to avoid bias.

10.2. Sample size and power calculations.

We propose to enroll a total of 270 patients evenly randomized into two groups of 135 patients each. To determine power for **Hypothesis 1**, we will use a Student's t-test approach. From recent data from our administrative CR data base, we believe that the CBCR group will complete 21 ± 13 (mean + sd) visits over the course of the study. The test, with a two-sided 0.05 alpha level, will have 80% power to detect an increase of 4.5 visits. We believe this to be a clinically significant difference (5).

Also, for **Hypothesis 2**, our recent administrative data indicates that 24% of patients in our CBCR program complete 36 visits. A chi-squared test with a two-sided 0.05 alpha rate and 135 subjects per group will have 80% power to detect an **increase to 39.8% or more in the HYCR group** (effect size=15.8 percentage point increase).

Hypothesis 3, 4 and 5 require longitudinal measures six months after CR is completed, so it is possible that some lost to follow-up will occur at follow-up testing point number 2. If we assume that no more than 20% will be lost, our sample size for this analysis will be at least 108. We anticipate a standard deviation of the change in meters walked in the 6-minute walk to be 107 meters (based on data from the Henry Ford Core Exercise Laboratory) When the sample size in each group is 108, a two group 0.05 one-sided t-test will have in excess of 90% power to reject the null hypothesis that the CBCR and HYCR groups are not equivalent (the difference in means is 50 meters or farther), in favor of the alternative hypothesis that the means in the two groups are equivalent.

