The measured of peak VO₂ should have a standard deviation near 6 (86). With a sample size of 108 per group, a two-group one-sided t-test will have greater than 80% power to reject the null hypothesis that the CBCR and HYCR groups are not equivalent (the difference in means is 2.0 mL/kg/min or farther), in favor of the alternative hypothesis that the means in the two groups are equivalent.

Based on Campbell, et al. (87), we anticipate that the standard deviation of the Short Form Health Survey (SF-12) physical component summary will be 22 and the mental component summary will be 18. When the sample size in each group is 108, a two-group 0.05 one-sided t-test of the physical component scale will have 80% power to reject the null hypothesis that the

CBCR and HYCR are not equivalent (the difference in means is 7.5 or further from zero in the same direction), in favor of the alternative hypothesis that the means of the two groups are equivalent. The power for the mental component summary will exceed 90%.

10.3. Data Analysis Plan.

Data analysis will begin with preparatory activities such as checking for complete data entry, identification of outliers, and other such data cleaning tasks. Once the above tasks are completed, the data base will be “locked” for analyses. The Statistical Analysis System, (SAS, version 9.4) will be used for data analysis. A detailed descriptive analysis of all quantitative data will be performed involving the summarization of data and the use of inferential and graphical exploratory analytic techniques. The information obtained from this preliminary investigation will be used to: 1) describe univariate and bivariate sample distributions of the data; 2) identify the interrelationships between variables (i.e., need for covariate adjustment); and 3) check for violations of assumptions underlying identified statistical techniques (e.g. independence, linearity, homoscedasticity, normality). In the event that statistical assumptions are severely violated, data transformations or nonparametric methods will be employed. An intention to treat approach will be utilized for all analyses. For hypothesis 1 the number of visits completed before lost to follow up will be used and for hypothesis 2 a yes/no response will be generated based on the observed data.

R33- Primary Aim: Assess the effect of a HYCR program on over-all patient attendance

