For the **Primary Hypothesis** (number of sessions completed), if the distribution of the number of sessions completed is normal then a Student’s t-test will be used for comparison of the two groups. In the likely event it is skewed a two-sample Wilcoxon with a Fligner-Policello correction for unequal variances will be used. **Hypothesis 2** (percentage of patients completing 36 CR sessions) will be addressed using a Chi-squared test for comparison of proportions.

R33- Secondary Aim: Assess the effect of HYCR on exercise capacity and quality of life.

Hypotheses 3 and 4 (both address measures of exercise capacity) and **Hypothesis 5** (QOL) all involve assessing if the two group responses are equivalent. A two one-sided test approach will be used to demonstrate equivalence between the two groups.

There are several identified **exploratory aims** for this project, including but not limited to:

- (a) short-term (6 month) retention of CR-related outcomes [e.g., exercise capacity, QOL, and self-engaged (not CR) purposeful exercise and total physical activity habits]
- (b) program cost effectiveness.

Analyses of the exploratory aim associated with the short-term retention of CR-related outcomes will be analogous to the analyses described above, such that Student's t-test, Chi-squared tests or their nonparametric alternatives will be utilized.

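### Section 10.2 gives the power of one one-sided t-test, but 10.3 plans two one-sided tests; on the plan's own inputs peak VO2 has about 57% power for equivalence, not more than 80%

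*Combined protocol and SAP*

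**What the plan says.** Section 10.2 takes 108 evaluable patients per group (135 less 20% loss) and gives the power for each secondary outcome in terms of one one-sided t-test.

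- **6-minute walk (Hypothesis 3):** SD of change 107 m, margin 50 m; "a two group 0.05 one-sided t-test will have in excess of 90% power to reject the null hypothesis" of non-equivalence.
- **Peak VO2 (Hypothesis 4):** SD near 6, margin 2.0 mL/kg/min; "With a sample size of 108 per group, a two-group one-sided t-test will have greater than 80% power". This sentence gives no alpha.
- **SF-12 physical summary:** SD 22, margin 7.5; "a two-group 0.05 one-sided t-test of the physical component scale will have 80% power". The null hypothesis is described as "the difference in means is 7.5 or further from zero in the same direction".
- **SF-12 mental summary:** SD 18; "The power for the mental component summary will exceed 90" per cent.

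In each case the alternative is said to be that the two group means are equivalent.

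Section 10.3 then commits Hypotheses 3 to 5 to a different procedure: "A two one-sided test approach will be used to demonstrate equivalence between the two groups". Section 2.2 words all three hypotheses as equivalence but adds, in brackets, that this means not inferior.

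**The concern.** Two one-sided tests establish equivalence only when both reject, that is, when the 90% confidence interval lies wholly inside the margins (at 0.05 per side). Power for that joint event is always lower than the power of one component test. When one test has 80% power and the true difference is zero, the joint power is only about 60%. If 10.2 powered one test while 10.3 runs two, the stated power does not belong to the planned analysis.

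This matters most for peak VO2. Section 3.3 says that programs need assurance of equivalent outcomes before they adopt the hybrid model. If the real chance of showing equivalence is well below the stated one, a failure to show it could be read as evidence against hybrid delivery when the test was simply underpowered.

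**Working it through.** **Inputs, all from 10.2 unless noted**

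- n = 135 × (1 − 0.20) = 108 per group.
- SD and margin: 6-minute walk 107 and 50; peak VO2 6 and 2.0; SF-12 physical 22 and 7.5; SF-12 mental 18 and 7.5.
- Alpha 0.05 per one-sided test. This is stated for the 6-minute walk and SF-12 and assumed for peak VO2.
- True difference 0. This is assumed, and it is the most favourable case for equivalence.

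**Formulas**

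- SE = SD × √(2/n).
- One one-sided test, normal approximation: power = Φ(margin/SE − 1.645).
- Two one-sided tests at true difference 0: power = 2Φ(margin/SE − 1.645) − 1.
- The exact values below use the noncentral t (214 df) for one test. For two tests they integrate over the distribution of the pooled variance.

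**Peak VO2, step by step**

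- SE = 6 × √(2/108) = 0.816, and margin/SE = 2.0/0.816 = 2.449.
- One test: Φ(2.449 − 1.645) = Φ(0.804) = 78.9%; exact 78.7%. A single test reaches 80% at an SD of 5.89, so the plan's figure is in effect reproduced by one test with an SD near 6.
- Two tests: 2 × 0.7895 − 1 = 57.9%; exact 57.4%. A simulation of 400,000 draws gave 57.6%.

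**All four outcomes, exact, 108 per group**

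| Outcome | Stated | One test | Two tests |
|---|---|---|---|
| 6-minute walk | >90% | 96.2% | 92.5% |
| Peak VO2 | >80% | 78.7% | 57.4% |
| SF-12 physical | 80% | 80.3% | 60.6% |
| SF-12 mental | >90% | 92.0% | 84.1% |

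The two SF-12 figures match a single test and not two. The 6-minute walk claim is true under both.

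**Sensitivity for peak VO2 under two one-sided tests**

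- No loss, 135 per group: 72.3%.
- 108 per group with a looser 0.10 per side: 75.5%.
- 108 per group, true difference 0.5 mL/kg/min: 49%.
- 108 per group, by SD: 80.1% at 5.0, 69.2% at 5.5, 61.0% at 5.85, 45.8% at 6.5.
- Evaluable patients needed for 80% at SD 6: 155 per group, more than the 135 randomised.

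**The case against.** The strongest objection concerns the SD. Hypothesis 4 is about improvement, and 5.2 speaks of change. Section 10.2 gives an SD of 6 for peak VO2 itself, citing a paper whose title refers to patients entering rehabilitation, whereas for the 6-minute walk it gives an SD of change. If 6 is the SD at each visit, the SD of change is 6 × √(2(1 − ρ)), where ρ is the correlation between visits. At 108 per group, two-test power is then 32% at ρ = 0.3, 57% at 0.5, 72% at 0.6, 80% at 0.65 and 87% at 0.7. Power for Hypothesis 4 could therefore lie on either side of 80%. This stands as a limit on the 57%. It does not rescue the stated figure, because the plan gives no correlation or SD of change for peak VO2.

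Second, 108 may be too low. Section 10.2 justifies it by saying "Hypothesis 3, 4 and 5 require longitudinal measures six months after CR is completed", yet 5.2 places these endpoints at completion of rehabilitation and lists the 6-month measures as exploratory. This also stands, but at SD 6 full retention brings power only to 72.3%.

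Third, the bracketed wording in 2.2 may mean that non-inferiority was intended, and a one-sided calculation would suit that. The error would then lie in 10.3 rather than 10.2. One of the two sections is wrong on either reading.

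Fourth, the SF-12 results say nothing about Hypothesis 5, which is defined on the Dartmouth COOP; the SF-12 is not in the visit schedule in 4.8. That is correct. They serve here only to show which test was powered.

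**Conclusion.** The concern holds. Section 10.2 reports single one-sided test power as power to show equivalence, while 10.3 requires both tests to reject. On the plan's own inputs peak VO2 has 57.4% power against a stated figure above 80%. The trial would then miss equivalence on Hypothesis 4 about 4 times in 10 (1 − 0.574 = 0.426) even if the two arms were truly identical.

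The figure assumes 108 evaluable per group, 6 as the SD of change, 0.05 per side and a true difference of zero. The mismatch itself depends on none of these. The 6-minute walk power, the primary hypothesis and the sample size of 270 are not affected. This should be corrected, but it does not threaten the main result.

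**What to change.** State one objective for Hypotheses 3 to 5, in the same terms, in 2.2, 10.2 and 10.3.

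- **If equivalence is kept:** remove the non-inferiority gloss from 2.2 and restate the power in 10.2 for two one-sided tests. With the current inputs this is about 57% for peak VO2 and 92% for the 6-minute walk. If the SF-12 figures stay, they become about 61% (physical) and 84% (mental).
- **If non-inferiority is meant:** change 10.3 to one one-sided test of the unfavourable confidence limit against the margin. The stated powers then roughly stand, with peak VO2 at about 79%.

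Before recomputing, settle two inputs: whether the peak VO2 SD of 6 is an SD of change, and whether the analysis uses follow-up visit 1 or the 6-month visit, with the expected loss at that visit. For Hypothesis 5, give an SD and margin for the Dartmouth COOP or say that its power was not calculated.

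The cost is wording and restated figures, with no extra patients. If equivalence is kept, the stated power for Hypothesis 4 falls below 80% unless an SD of change of about 5.0 or less can be justified at 108 per group (about 5.6 or less at 135).

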2.2 Secondary Aims

R33 Phase: Assess the effect of HYCR on exercise capacity and quality of life.

Hypothesis 3: The improvement in exercise capacity, as measured by distance walked during the six min walk (6MW) test, in patients randomized to HYCR will be equivalent (not inferior) to patients randomized to CBCR.

Hypothesis 4: The improvement in exercise capacity, as measured by peak oxygen uptake (VO₂), in patients randomized to HYCR will be equivalent (not inferior) to patients randomized to CBCR.

Hypothesis 5: The improvement in quality of life (QOL), as measured by the Dartmouth COOP, in patients randomized to HYCR will be equivalent (not inferior) to patients randomized to CBCR.

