4.3.3. Subject Enrollment

4.3.3.a. Screening ... from in-patient and EMR

Using census data from the EMR for in-patient cardiology units, as well as the out-patient preventive cardiology unit work que in the EMR, potential subjects will be identified/screened by the CR and research staff that visits or calls patients. The names of potential candidates will be forwarded to the research staff who will then conduct a detailed screening of eligibility using the EMR and a telephone call. If the patient meets the enrollment criteria and agrees to participate after having discussed study purpose, procedures, risks and responsibilities, a baseline appointment will be made, ideally on the same day the patient will be scheduled to attend CR orientation; 7-14 days after discharge if hospitalized. Patients stating interest in the research study will meet with the research coordinator, the project PI, or the project manager to undergo further screening and receive a verbal explanation of the trial and sign informed consent.

4.3.3.b. Baseline Clinic Visit

The baseline testing required in this protocol should be completed as soon as possible after signed consent, but may be completed up to 4 weeks after consenting, if necessary. All baseline testing will be completed prior to a patient's first session in CR. For any study visit that includes a QOL assessment and a symptom-limited cardiopulmonary exercise (CPX) test, the quality of life (QOL) instrument(s) (Dartmouth COOP, and/or EuroQOL-5D) must be completed prior to the CPX test. Also, the 6 min walk (6MW) test must be completed, per standardized procedures (84), 1 hour or more before the CPX test; therefore, during any clinic visit the order of these tests is as follows: (a) 6MW, (b) QOL tools and other assessments (PHQ-9, Rate your Plate, mini-cog), (c) 5x repetition sit-to-stand test, and (d) CPX test. The 6MW and the CPX test will be completed per procedures as specified and overseen by the Henry Ford Clinical Exercise Physiology Core Laboratory ("Exercise Core Lab"); and case report forms for 6MW and QOL surveys and data collected from the CPX test will be forwarded to the Exercise Core lab or data entry/management as indicated.

4.3.3.c. *Baseline Testing*

The written questionnaires (EuroQOL-5D, Dartmouth COOP, Rate Your Plate, and PHQ-9) will be administered per the standardized instructions associated with each instrument.

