4.8. Subject Follow-Up

After completing CR or a subject’s last CR visit, follow-up visits 1 and 2 will be scheduled, the former scheduled within 10 days of last CR visit and the latter scheduled at 6 months \pm 15 days after last CR visit. Data collected at follow-up visit one will be nearly the same as that gathered during baseline. This includes both QOL instruments (Dartmouth COOP, EQOL), a CPX test, the 6MW, PHQ-9, Rate your Plate, and 5x sit-to-stand. Data collected at follow-up visit two includes both QOL instruments (Dartmouth COOP, EQOL), a CPX test, the 6MW, PHQ-9, Rate your Plate, and frailty assessment.

Table 4. Schedule of Trial Events and Time line

Patient Care Event	Screening and Baseline	Weeks 1-26 or CR visits 1-36*	F/up visit 1 within 10 d after last CR visit	2 mo after last CR visit	4 mo after last CR visit	F/up visit 2 at 6 mo after last CR visit
Testing						
CPX	X		X			X
6MW	X		X			X
Dartmouth COOP	X		X			X
EuroQOL-5D	X		X			X
Rate your plate	X		X			X
Mini-cog	X					
5x sit-to-stand	X		X			X
iPAQ	X		X	X	X	X
PAST	X		X	X	X	X
Training						
Exercise sessions		X				
Telephone calls				X	X	

*Patients will have 6 mo to complete 36 visits; iPAQ=International Physical Activity Questionnaire; PAST = Past-day Adult Sedentary Time Questionnaire

5. Trial Endpoints

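### Hypothesis 5 tests the Dartmouth COOP, but its only margin, SDs and power figures belong to the SF-12, which is on no assessment list

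*Combined protocol and SAP*

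**What the plan says.** Section 2.2 states Hypothesis 5 in terms of one instrument: "The improvement in quality of life (QOL), as measured by the Dartmouth COOP". Table 3 lists the same instrument as the QOL outcome used for the trial.

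The assessment sections agree with this. For baseline, section 4.3.3.b says that "the quality of life (QOL) instrument(s) (Dartmouth COOP, and/or EuroQOL-5D) must be completed prior to the CPX test", and section 4.3.3.c lists the written questionnaires as EuroQOL-5D, COOP, Rate Your Plate and PHQ-9. For follow-up visit 1, section 4.8 says "This includes both QOL instruments (Dartmouth COOP, EQOL), a CPX test, the 6MW"; it names the same two QOL tools for follow-up visit 2. Table 4 schedules the COOP and EuroQOL-5D and no other QOL instrument.

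Section 10.2 then plans the QOL comparison on the SF-12:

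- SD, physical: "we anticipate that the standard deviation of the Short Form Health Survey (SF-12) physical component summary will be 22"
- SD, mental: "the mental component summary will be 18"
- Margin, as the null hypothesis: "CBCR and HYCR are not equivalent (the difference in means is 7.5 or further from zero in the same direction"
- Power, physical: "a two-group 0.05 one-sided t-test of the physical component scale will have 80% power"
- Power, mental: "The power for the mental component summary will exceed 90" percent

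Apart from this paragraph, the SF-12 appears only in the list of abbreviations. Section 10.3 assigns two one-sided tests to Hypotheses 3 to 5 and gives no margin. Section 5.2 names the endpoint only as a change in quality of life.

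**The concern.** In an equivalence test the margin is the hypothesis. A superiority test has zero as its default null, but two one-sided tests cannot be computed until someone states how large a difference, in the endpoint's own units, would still count as equivalent. The only QOL margin in the plan is 7.5 points on SF-12 summary scores. Nothing converts it to the COOP, and the documents do not say which COOP score is tested or which direction is better.

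An analyst who follows the plan as written can carry 7.5 over to a scale it was not set for, or choose a COOP margin at analysis. The first has no justification. The second loses control of the error rate if the choice comes after results are visible, and section 7.3 gives the analysing biostatistician the treatment codes. Equivalence of outcomes also carries weight here: section 3.3 says that programs considering a hybrid model need to be assured of it.

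**Working it through.** **Inputs.** 135 randomized per group and at most 20% lost (section 10.2), so 135 × 0.80 = 108 per group. Margin 7.5; SDs 22 and 18; one-sided alpha 0.05 (section 10.2). Two one-sided tests planned (section 10.3). The true difference is taken as zero throughout.

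**Step 1: reproduce the plan's figures.** SE = SD × √(2/108) = SD × 0.1361. Power of one one-sided test = Φ(7.5/SE − 1.645).

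| SF-12 summary | SE | 7.5/SE | Power (normal) | Power (noncentral t) | Stated |
|---|---|---|---|---|---|
| Physical, SD 22 | 2.994 | 2.505 | 80.5% | 80.3% | 80% |
| Mental, SD 18 | 2.449 | 3.062 | 92.2% | 92.0% | above 90% |

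Both reproduce. The calculation is correct for a single one-sided test on the SF-12; the fault is that it concerns the wrong instrument.

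**Step 2: what carries over to the COOP.** Power depends on the margin divided by the SD of change. For the SF-12 this ratio is 7.5/22 = 0.34 (physical) and 7.5/18 = 0.42 (mental, taking the same 7.5 for both). For the COOP neither the numerator nor the denominator is given, so its power cannot be computed.

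**Step 3: the ratio the COOP would need.** At 108 per group, for 80% power:

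- one one-sided test: (1.645 + 0.842) × √(2/108) = 2.487 × 0.1361 = 0.34 SD
- two one-sided tests: (1.645 + 1.282) × √(2/108) = 2.927 × 0.1361 = 0.40 SD

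**Step 4: power over an assumed range of ratios.** With r = margin/SD, one-sided power is Φ(r/0.1361 − 1.645). Power of the two one-sided tests is 2Φ(r/0.1361 − 1.645) − 1, floored at zero.

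| Margin/SD (assumed) | One one-sided test | Two one-sided tests |
|---|---|---|
| 0.20 | 43% | 0% |
| 0.25 | 58% | 15% |
| 0.30 | 71% | 42% |
| 0.40 | 90% | 80% |
| 0.50 | 98% | 96% |

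**Step 5: the planned test on the SF-12's own figures.** Two one-sided tests give 2 × 0.8052 − 1 = 61% (physical) and 2 × 0.9218 − 1 = 84% (mental). The stated 80% and above 90% would therefore not describe the section 10.3 test even if the SF-12 were collected.

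**Step 6: dependence on n.** The 108 comes from loss at follow-up visit 2, whereas section 5.2 places the secondary QOL endpoint at completion of CR. With all 135 per group evaluable, √(2/135) = 0.1217 and the thresholds in step 3 fall to 0.30 and 0.36 SD. This does not supply a COOP margin.

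**The case against.** The strongest reply is that this is a secondary hypothesis and that little else depends on it. That is correct. Section 8.1 ties the 270 subjects to the primary hypothesis. Section 10.2 reports power for Hypothesis 5 at the number that results, so replacing the SF-12 paragraph changes neither enrollment nor the tests of Hypotheses 1 and 2. The SF-12 arithmetic is also right, so this is an inconsistency and a missing margin, not a miscalculation.

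A second reply is that a COOP margin can still be fixed in time, since section 7.1 has the Steering Committee approve the main analysis plan and vote on amendments. That route exists, and using it would cure the problem. But nothing in the plan requires that step or supplies the margin.

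A third is that the manual of operations, which is to cover survey tools (section 9), might include the SF-12, and that Table 4 is not exhaustive because it omits the PHQ-9. The strict claim is therefore that the SF-12 is on no assessment list in these documents. Section 4.8, however, refers to both QOL instruments and names the two, which reads as a closed list. Even if the SF-12 were given, Hypothesis 5 would still name the COOP and still have no margin.

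Finally, the SF-12 might be meant as a planning stand-in. The text does not say so, and a stand-in SD would not provide a COOP margin.

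**Conclusion.** The concern holds. Every planning figure for Hypothesis 5 (two SDs, one margin, two powers) belongs to an instrument on no assessment list. As written, the equivalence test of the COOP has no margin, and the stated power does not apply to it.

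The true power is unknown. Over assumed margins of 0.20 to 0.50 SD it runs from 0% to 96% for the planned test at 108 per group, with 80% reached at about 0.40 SD. These figures assume a true difference of zero, one-sided alpha of 0.05, equal groups, and 20% loss as stated in the plan.

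This must be fixed before analysis, because a named hypothesis currently has no defined test. The primary endpoint, its power and the enrollment target are not affected.

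**What to change.** Replace the SF-12 paragraph in section 10.2 and add the margin to section 10.3:

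1. Name the COOP score that Hypothesis 5 tests, the direction that means improvement, and the visit at which it is assessed.
2. Estimate the SD of change from the program's own before-and-after COOP records. Table 3 and section 10.3 describe the COOP as routinely assessed before and after CR; how complete those records are would need checking.
3. State a COOP margin in points, with its justification, and have it approved before any unblinded look at the data.
4. State power for the test that will be run (two one-sided tests, if section 10.3 stands) at the n expected at that visit.
5. Delete the SF-12 power claims.

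The cost is SAP wording and one calculation, with no new visits or patients. The downside is that the restated power may fall below 80%, which should then be reported as it is.

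The alternative is to make the SF-12 an administered endpoint and bring the hypothesis, the schedule and section 10.2 into line. That adds a questionnaire, leaves anyone already enrolled without a baseline value, and still requires the power to be restated: on the plan's figures the physical summary would have 61% power for two one-sided tests at 108 per group, and would need 148 evaluable per group for 80% (2 × 2.927² × (22/7.5)² = 147.4, rounded up).
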